Appendix 1: Gantt Framework

Image: Normeter in the serie of th																																									
10 10 <th< td="">		Nove	mber			Dece	mber			Jan	uary			Feb	ruary			Ma	arch			A	pril			N	lay			Ju	ne			Ju	ly			Aug	gust		</th<>			Nove	mber			Dece	mber			Jan	uary			Feb	ruary			Ma	arch			A	pril			N	lay			Ju	ne			Ju	ly			Aug	gust	
Protocol P		Q1	Q2	Q3	Q4	Q1	Q2	Q3	Q4	Q1	Q2	Q3	Q4	Q1	Q2	Q3	Q4	Q1	Q2	Q3	Q4	Q1	Q2	Q3	Q4	Q1	Q2	Q3	Q4	Q1	Q2	Q3	Q4	Q1	Q2	Q3	Q4	Q1	Q2	Q3	Q4
Crain Crain <td< td="">Protocol																																									</td<>	Protocol																																								
Interfactor	Creation																																								 
This Bugaled <t< td="">Ethics UK																																									</t<>	Ethics UK																																								
Gram Image: Control in the control	Ethics Bangladoch																																								
Application	GCRE																																								
Tandado / Image: Solution of Look I	Application																																								
tob	Translation of																																								
Dhala codyb Image: Cody b Image: Cody b tools		tools																																								
Recurrent Resultant	Dhaka icddr,b meeting																																								
of Base	Recruitment									1																															
Participant Recuritment I	of RAs																																								
Recruitment I <td< td="">Participant																																									</td<>	Participant																																								
and Section I <td< td="">Recruitment																																									</td<>	Recruitment																																								
Nound 1047a Image: Collection Image: C	and Selection																																								
Round 1 Ab Mork <td< td="">Collection																																									</td<>	Collection																																								
NUM. Image: Constraint of the constrai	Round 1 Lab																																								
Nound 2 Date Round 2 Date Round 1 Data		Round 1 Data																																								
Round 1 Data Analysis Round 1 Data Disemination (Abstract) Round 2 Data Preparation Round 2 Data Officiencienciencienciencienciencienciencie	Verification																																								
Analysis Analysis <th< td="">Round 1 Data																																									</th<>	Round 1 Data																																								
Round 1 Data Dissemination (Abstract) Round 2 Preparation Round 2 Data Collection Round 2 Data Round	Analysis																																								
Dissemination (Abstract) Image: Constraint of the constrain	Round 1 Data																																								
Round 2 Preparation Round 2 Data Collection Nound 2 Data Collection Nound 2 Data Nound 2 Data <td< td="">Dissemination (Abstract)																																									</td<>	Dissemination (Abstract)																																								
None 2	Round 2											1																													\vdash
Round 2 Data Collection Round 2 Lab Work Now 2 Data Work Round 2 Data Round 2 Da	Preparation																			1	1	1		1	1																
Collection	Round 2 Data		1								1									1	1	1		1	1			1													
Round 2 Lab Work Round 2 Data Verification Round 2 Data Analysis Round 2 Data Analysis Round 2 Data Analysis Round 2 Data Analysis Round 2 Data Data Round 2 Data Data Round 2 Data Data Round 2 Data Dispensioning Round 2 Data Dispensioning Round 2 Data Dispensioning Round 2 Data Round 2 Data Dispensioning Round 2 Data	Collection	ļ										 		L			ļ																				ļ				
Work O	Round 2 Lab																																								
Nound 2 Data Verification Image: Constraint of the constraint o	Work		 				 				 	 								 	 	 		 	 			 													\vdash
Round 2 Data Analysis Image: Constraint on the constraint o	Round 2 Data Verification									1																															
Analysis	Round 2 Data																																								
Round 2 Data	Analysis	ļ										 		L			ļ																		L						
	Round 2 Data																			1	1	1		1	1																
	Dissemination (Manuscript)																																								

Appendix 2: Budget

- Laboratory work: 129 USD per test X 120 = 15,480 USD (12,090 GBP)
- Faecal occult tests: 50 GBP for 100
- Research Assistants: 60 GBP per week X 6 weeks X 4 RAs = 1,440 GBP (salary based on interpreter salary from NGOs in Cox's Bazar)
- RA local travel: 4 RAs X 28 days X 2 GBP per day = 230
- Equipment: 100 GBP Lenovo Tab8 Tablet X5 = 500GBP
- Travel for [name]: 2870 GBP
- Two surveillance visits for icddr,b: 1094 USD = 855GBP
- Stool Sample Shipping: 12USD * 2 shipments = 24USD = 19GBP
- Icddr,b admin support fee: 1950 GBP

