Households will be randomised in a 1:1 ratio into the basic survey, a survey asking if a child had diarrhoea and dysentery in the past two weeks, based on DHS survey measures; and the enhanced survey, based on qualified stool charts (of which images will be displayed on the tablet during surveying), proxies for diarrhoea (such as oral intake), and measures of waterwashed diseases. All households will also be administered a basic demographic survey with questions on education, health, living environment, and WASH usage. If a household reports dysentery, they will be given the information of a local clinic for treatment. All surveys will be translated into Rohingya, and back translated into English – with translation following WHO guidelines: aiming for the simplest translation with the conceptual equivalent, targeted toward the target audience or Rohingya refugees, many of whom are illiterate with a low level of education. This will be done through consultation with Rohingya community members to ensure proper translation.

Data collection will take place at two time points: February/March and June/July. Research assistants will collect data through the use of ODK on an Android tablet. Data will be stored on the tablets and uploaded to Warwick servers at the end of each day, when research assistants return to the base office. Data will be additionally verified daily.

Stool sampling

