Within each arm at each time point, 20 households reporting diarrhoea, and 20 not reporting diarrhoea, will be selected to have the oldest infant under 5 undergo stool testing - a total of 80 households at each time point, 160 in total. The first 20 households reporting diarrhoea and not reporting diarrhoea in each arm will be selected and asked if they are willing to provide stool samples. A WhatsApp group will be created for the research assistants to determine when 20 consenting households have been reached in each arm. The consenting households will be given a stool collection container once the survey has been administered, which will be collected the following day. All stool containers will be labelled with a barcode which will be scanned by the research assistant using a tablet, to link the stools sample with the survey. Stool will be collected by the carer, and tested for the presence of predetermined organisms which are endemic to the Rohingya population, along with a small number of select pathogens that are not endemic (Table 1); and for the presence of biological markers of infection: calprotectin and lactoferrin. This will be done through the use of polymerase chain reaction analysis (PCR) at the laboratory at the ICDDR,B in Dhaka, Bangladesh. Stool will also be tested for blood using a faecal hemooccult test.

Туре	Species	Carriage period (adults)	Carriage period (children)
Bacteria	Shiga toxin-producing Escherichia	17-18 days (1)	35-69 days (2)
	Enteropathogenic Escherichia coli	ND	20—36 days (2)
	Enterotoxigenic Escherichia Coli	ND	<5 days (2)
	Enteroinvasive Escherichia Coli	ND	ND
	Enterohemorrhagic Escherichia Coli	ND	2-62 days (2)
	Salmonella typhi	12-25 days (3)	Varies (2)
	Salmonella paratyphi	28-55 days (4)	~30 days (2)
	Campylobacter	14-21 days (5)	Up to 6 weeks (5)
	Shigella	~28 days (6)	1-10 days (6)
	Cholera	~2 days (7)	~4 days (7)
	C. difficile	6-57 days (8)	6-57 days (8)
	C. perfringens	ND	ND
	Acinetobacter	7-11 days (9)	ND
Protozoa	Entamoeba histolytica	ND	ND
	Cryptosporidium	~8 days (10)	~8 days (10)
	Cyclospora	5-13 days (11)	22-23 days (11)
	Giardia	2-6 weeks (12)	~6 months (13)
Helminth	Ancylostoma duodenale	1-2 years (14)	ND
	Ascaris lumbricoides	Years (15)	Years (15)
Viruses	Rota-virus	Up to 35 days (16)	4-57 days (2)
	Hepatitis A	~21 days (17)	Up to 21 days (12)
	Hepatitis E	3-4 weeks (18)	ND
	Norovirus	ND	8-60 days (19)
	Human Caliciviruses	~14 days (20)	~12 days (20)
	Adenovirus	ND	8-23 days (20)

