	Astrovirus	ND	1-10 days (20)
Fungi	Enterocytozoon	18-38 days (21)	9-40 days (22)

Informed consent

All respondents will be consented in the Rohingya language and given a demographic and behaviour survey at the first time point. All questionnaires and surveys will be translated into Rohingya and back translated into English, with all data collection will be completed by Rohingya research assistants.

Data analysis

Data will be analysed using Stata version 15. The following analyses will be conducted

- Incidence rate ratios and associated 95% confidence intervals comparing diarrhoea and dysentery incidence between:
 - o Enhanced and basic surveys
 - o Survey method and stool analysis method
- Positive predictive value and associated 95% confidence interval of reported diarrhoea for the presence of enteric pathogens
- The association between diarrhoea presence and other potential markers of enteric infection such as MUAC and water-related diseases, measured for example by Jaccard's index
- A logistic regression of diarrhoea prevalence on demographic and health variables to examine association.

All missing data will be reported and assumed to be missing at random. The sample sizes proposed here would give us power to estimate the self-reported diarrhoea rate in each arm to a 95% confidence interval of approximately ±4 percentage points, assuming a point prevalence of 10%. We would also be able to estimate the positive and negative predictive values to approximately ±7 percentage points assuming values of 90%.

Data Management

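### The protocol plans 160 stool-tested households but its laboratory budget line covers 120 tests, and the stated ±7-point precision matches the larger number only

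*Protocol*

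**What the plan says.** All references are to the protocol.

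- **Design.** Diarrhoea survey: "Households will be randomised in a 1:1 ratio into the basic survey" or the enhanced one, and "Data collection will take place at two time points: February/March and June/July". Stool sampling: "Within each arm at each time point, 20 households reporting diarrhoea, and 20 not reporting diarrhoea, will be selected" for stool testing, which the same section totals as "a total of 80 households at each time point, 160 in total".
- **Use of the samples.** The Executive Summary names the positive and negative predictive values of self-reported diarrhoea as the primary outcomes. They can be computed only from stools that are tested.
- **Precision.** Data analysis says that the proposed sample sizes allow both predictive values to be estimated "to approximately ±7 percentage points assuming values of 90" per cent.
- **Budget.** Appendix 2 lists "Laboratory work: 129 USD per test X 120 = 15,480 USD (12,090 GBP") and, on the next line, "Faecal occult tests: 50 GBP for 100". It also lists two stool shipments.
- **Occult blood.** Stool sampling adds: "Stool will also be tested for blood using a faecal hemooccult test". No subset is named.

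**The concern.** The sampling plan and the laboratory line imply different numbers of tested stools, and nothing in the protocol links them: no subset for testing, no allowance for refusals, no second funding line. The figure of 120 matches neither one round (80) nor both (160), and the two shipments, together with separate laboratory work for each round in Appendix 1, indicate that the budget covers both rounds.

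At stake is the size of the sample behind the primary outcomes. If 120 is what will be tested, the precision statement is slightly too optimistic and the quota of 20 per cell cannot be met in every cell. If 160 will be tested, the laboratory line is too low. A separate statistical analysis plan would not settle this, because both numbers stand in the protocol and one of them is a cost.

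**Working it through.** **Inputs**
- 20 households per report group, 2 report groups, 2 arms, 2 time points (Stool sampling; Diarrhoea survey).
- 129 USD per test, 120 tests, 15,480 USD, 12,090 GBP (Appendix 2).
- Predictive values of 90% and a half-width of about ±7 points (Data analysis). The 95% level is stated there for the diarrhoea rate and for the positive predictive value; I take it to apply to the ±7 figure as well.
- Assumption: one budgeted test covers one stool sample.

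**1. Sample count.** 20 × 2 × 2 × 2 = 160, as the protocol states.

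**2. Budget line.** 129 × 120 = 15,480 USD, as stated. The product is right, so 120 is not a slip in the total.

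**3. Gap.** 160 − 120 = 40 tests, and 40/160 = 25%. Cost of 160 tests: 129 × 160 = 20,640 USD. Difference: 20,640 − 15,480 = 5,160 USD. At the protocol's implied rate, 12,090/15,480 = 0.781 GBP per USD, the difference is about 4,030 GBP.

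**4. The protocol's precision figure.** Half-width = 1.96 × √(p(1 − p)/n) with p = 0.90. Half of the 160 stools come from reporting households and half from non-reporting ones, so pooled over arms and rounds n = 80 per predictive value:

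1.96 × √(0.09/80) = 6.6 points, which rounds to the stated ±7.

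The companion figure for the diarrhoea rate reproduces in the same way: 1.96 × √(0.09/200) = 4.2 points, against the stated ±4.

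**5. The same calculation with 120 tests, split evenly**

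| Estimate | 160 tests | 120 tests |
|---|---|---|
| Pooled over arms and rounds | n = 80, ±6.6 | n = 60, ±7.6 |
| Per survey method, both rounds | n = 40, ±9.3 | n = 30, ±10.7 |

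**6. Tests needed for ±7.** For exactly 7.0 points: n = 1.96² × 0.09/0.07² = 70.6, so 71 per predictive value, or 142 tests. For a value that still rounds to 7 (below 7.5): n = 1.96² × 0.09/0.075² = 61.5, so 62 per predictive value, or 124 tests. A total of 120 misses both, the second narrowly.

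**7. Occult blood.** 160 − 100 = 60 more stools than listed tests, or 120 − 100 = 20 more if 120 stools are tested.

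**The case against.** The strongest reply is that this is a housekeeping mismatch in a budget appendix. Data analysis says approximately ±7, the pooled loss is one point (±6.6 to ±7.6), and a cost quantity is not a sample-size statement. The size of the loss is fairly put. The mismatch remains, because it concerns how many primary-outcome measurements will be made.

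Four stronger readings are tempting, and the protocol does not support them.

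- **That the ±7 figure requires all 160 tests.** The design requires 160. The precision figure needs about 142, or 124 with rounding.
- **That the shortfall would fall on June/July.** If round 1 used its full 80 tests, 40 would remain, or 10 per arm-by-report cell: 1.96 × √(0.09/10) = ±18.6 points, against ±13.1 for the 20 per cell already planned. But no section says that tests are used in round order. Nor is a full round 1 assured: at the assumed 10% prevalence, 200 households per arm yield about 20 reporters, all of whom would have to consent, in what the Executive Summary calls the low-incidence season. The quotas are equal in both rounds, so higher incidence in June/July does not raise the number planned there.
- **That a quarter of the primary-outcome sample is unfunded.** Appendix 2 gives no total and does not say that it is the whole funding. The protocol shows only that the laboratory line does not cover the planned number.
- **That the occult-blood line is a second proven shortfall.** It may be a pack price; unlike the laboratory line, it does not multiply a unit cost by a planned quantity. Occult blood is not named as a primary outcome. It merits a check only.

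**Conclusion.** The inconsistency is real and small in effect. The protocol plans 160 stool-tested households, its laboratory line covers 120 tests, and the 40-test difference is unexplained. The stated precision reproduces with 160 (±6.6 points pooled). With 120 it becomes ±7.6, or about ±8, and ±10.7 instead of ±9.3 per survey method. Most of the width per method comes from the design and not from the budget, and the protocol promises no per-method precision for the predictive values.

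This rests on predictive values of 90%, a 95% Wald interval, an even split of tests over the cells, and one budgeted test per stool. Whether money for the other 40 tests exists elsewhere cannot be told from the protocol.

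**What to change.** Before round 1 testing, carry one number through Stool sampling, Data analysis and Appendix 2.

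- **Keep 160.** Correct the laboratory line to 129 × 160 = 20,640 USD, 5,160 USD (about 4,030 GBP) more, or name the source that pays for the other 40 tests. The precision statement can stand.
- **Use 120.** State 120 tests, keep the quotas equal at 120/8 = 15 per arm, round and report cell, and restate the pooled precision as about ±8 points at 90%. This costs only wording.

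In either case, confirm that the occult-blood tests cover the number of stools chosen. At the listed price (50/100 = 0.50 GBP each), 60 more would cost 30 GBP and 20 more would cost 10 GBP.

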Appendix 3: Sample Survey

Data Collection	Log Book (Sepa	arated Data					
Name							
Phone Number							
Household Barcode	e SCAN BARC	ODE					
Survey Data (Se	parate from Lo	g Book)					
RA	1	2	3	4			
EA	_	_	_	_			
Date							
Household	SCAN		•	•			
Barcode	BARCODE						

Resident Information (all respondents)

Name	Age	Sex	Education Level	Occupation	Health Conditions	Time Spent in Bangladesh	Relationship to Respondent
RESPONDANT							
SPOUSE IF PRESENT							
Child/Other Family							
Child/Other Family							
Child/Other Family							

Child/Other Family				
Child/Other Family				
Child/Other Family				

Household Information (all respondents)

What is the main source of drinking water for your household?	Piped water into home	Piped water into plot	Piped water to tap	Borehole	Dug well	Spring	Rain	Truck	Cart	Surface Water	Bottled Water
Where is that water source located	In my home	In my plot	In a public space								
How long does it take you to get there?		Minutes									
Do you share this with other households?	Yes	No									
	If yes, how many		Households								
	If yes, how long do you have to wait for water										
			Minutes								

Do you do anything to make this water safe to drink?	Yes	No									
	If yes, what?	Boil	Bleach/Chlorine	Cloth Strain	Filter	Solar disinfection	Sit and Settle	Other:			
Can I see where you use the toilet?	Yes	No									
	lf yes, describe:	Flush toilet to sewer	Pit Latrine	VIP Latrine	Flush toilet to Latrine	Composting Toilet	Bucket Toilet	Open Defecation	Other:		
How many people use this toilet		People									
Is this toilet separated by sex	Yes	No									
Do you feel safe using this toilet during the day?	Yes	No									
Do you feel safe using this toilet when dark?	Yes	No								_	
How do you wash your hands?	Water alone	Water with Soap	Alcohol Based Sanitizer	Non- Alcohol Based Sanitizer	Does not wash hands	Other:					
When do you wash your hands? (all that apply)	After Defecation	After cleaning a child's stool	Before Feeding a Child	Before Eating	Before preparing food	Other:					

Do you own livestock?	Yes		No							
Where do you normally seek healthcare?										
OBSERVE MATERIAL OF FLOOR	Natural Floor	Wood	Bamboo	Tarp	Finished Floor	Other:				
OBSERVE MATERIAL OF ROOF	No roof	Thatch	Bamboo	Wood	Cardboard	Tin	Ceramic	Cement	Tent	Other:
OBSERVE WATER STORAGE VESSEL	Open Bucket	Closed bucket	Bottle	Jerry Can	Bucket	Other:				

Basic Survey (50% of respondants)

IDENTIFY OLDEST CHILD UNDER 5

Has this child had 3 or more loose or watery stools any day in the past 2 weeks?	Yes	No
Has this child had blood in their stool in the past 2 weeks?	Yes	No

If yes to either, did you seek treatment for either of these?	Yes	No	
	lf yes, where?		

Enhanced Survey (50% of respondants)

IDENTIFY OLDEST CHILD UNDER 5												
Mid-Upper Arm Circumference			cm									
*SHOW AMSTERDAM	Consistency	А	В	С	D			_				
CHART*Has the child had any of these stools in the past 2 weeks	Colour	1	2	3	4	5	6					
How long ago?	1		2			3		4	5	6	7	Other:
How many times on the worst day?	1		2			3		4	5	6	7	Other:
How many days did it last?	1		2			3		4	5	6	7	Other:

References

- 1. Vonberg, Ralf P., et al. "Duration of Fecal Shedding of Shiga Toxin–Producing Escherichia Coli O104:H4 in Patients Infected During the 2011 Outbreak in Germany: A Multicenter Study." *Clinical Infectious Diseases*, vol. 56, no. 8, 2013, pp. 1132–1140., doi:10.1093/cid/cis1218.
- 2. ECDC. Systematic Review on the Incubation and Infectiousness/Shedding Period of Communicable Diseases in Children. 2016, Systematic Review on the Incubation and Infectiousness/Shedding Period of Communicable Diseases in Children, ecdc.europa.eu/sites/portal/files/media/en/publications/Publications/systematic-review-incubation-period-shedding-children.pdf.
- 3. Murase, T, et al. "Fecal Excretion of Salmonella Enterica Serovar Typhimurium Following a Food-Borne Outbreak." *JOURNAL OF CLINICAL MICROBIOLOGY*, vol. 38, no. 9, 2000.
- 4. Gunn, John S., et al. "Salmonella Chronic Carriage: Epidemiology, Diagnosis, and Gallbladder Persistence." *Trends in Microbiology*, vol. 22, no. 11, 2014, pp. 648–655., doi:10.1016/j.tim.2014.06.007.
- 5. Janssen, R., et al. "Host-Pathogen Interactions in Campylobacter Infections: the Host Perspective." *Clinical Microbiology Reviews*, vol. 21, no. 3, 2008, pp. 505–518., doi:10.1128/cmr.00055-07.
- 6. South Australia Health. "Shigella Infection Including Symptoms, Treatment and Prevention." SA Health, 2018, www.sahealth.sa.gov.au/wps/wcm/connect/public+content/sa+health+internet/health+topics/health+conditions+prevention+and+treatment/infe ctious+diseases/shigella+infection/shigella+infection+-+including+symptoms+treatment+and+prevention.
- 7. Weil, Ana A., et al. "Bacterial Shedding in Household Contacts of Cholera Patients in Dhaka, Bangladesh." *The American Journal of Tropical Medicine and Hygiene*, vol. 91, no. 4, 2014, pp. 738–742., doi:10.4269/ajtmh.14-0095.

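### The enhanced form prints no blood-in-stool item, although dysentery is to be compared between arms, and no rule says which enhanced-arm households count as reporting diarrhoea when stool donors are chosen

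*Protocol*

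**What the plan says.** The Data analysis section of the protocol lists incidence rate ratios with 95% confidence intervals "comparing diarrhoea and dysentery incidence between" the enhanced and basic surveys. Both outcomes are therefore needed in both arms.

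Appendix 3 prints two alternative forms, each for half of the respondents. The basic form has two yes/no items: "Has this child had 3 or more loose or watery stools any day in the past 2 weeks" and "Has this child had blood in their stool in the past 2 weeks". The enhanced form records mid-upper arm circumference (MUAC) and then asks, with a stool chart, "Has the child had any of these stools in the past 2 weeks", coded by consistency (A to D) and colour (1 to 6). It goes on to ask how long ago, "How many times on the worst day", and the number of days. It has no item worded for blood and gives no rule for turning these answers into diarrhoea yes or no.

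In the Diarrhoea survey section, the basic survey is described as covering diarrhoea and dysentery. The enhanced survey is described as stool charts plus "proxies for diarrhoea (such as oral intake), and measures of waterwashed diseases". The same section says, without restriction to an arm: "If a household reports dysentery, they will be given the information of a local clinic for treatment".

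The Stool sampling section takes, in each arm and round, the first 20 households that report diarrhoea and the first 20 that do not. Research assistants keep count through a messaging group.

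**The concern.** Two things are at stake.

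First, a between-arm dysentery ratio needs the same kind of report from both arms. If one arm is never asked about blood, the planned ratio has no comparable numerator there. The sentence on clinic information also presupposes a dysentery report that half of the households are not prompted to give.

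Second, the primary outcomes are the positive and negative predictive values of reported diarrhoea. They are estimated from households chosen for stool testing by whether they report diarrhoea. In the basic arm the yes/no item settles this. In the enhanced arm someone must turn a chart letter and a count into a status at the doorstep, and the protocol does not say how. Different research assistants may draw the line in different places, and the protocol gives no means of knowing where each drew it.

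**Working it through.** **1. Households per arm.** Sampling gives 400 households and the Diarrhoea survey section gives 1:1 allocation, so 400 / 2 = 200 per arm. This can be checked against the plan's own precision figure of about ±4 percentage points at 10% prevalence (Data analysis):

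half-width = 1.96 × √(p(1 − p)/n) = 1.96 × √(0.10 × 0.90 / 200) = 1.96 × 0.0212 = 0.0416

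That is ±4.16 points. The stated figure reproduces, so the plan itself works with 200 per arm.

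**2. The two forms side by side (Appendix 3).**

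| | Basic | Enhanced |
|---|---|---|
| Recall | 2 weeks | 2 weeks |
| Stool type | loose or watery, in the question | chart consistency A to D, colour 1 to 6 |
| Frequency | 3 or more, in the question | worst-day count, no threshold |
| Blood | yes/no | no worded item |
| Who is a case | a yes answer | not stated |

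**3. Dysentery.** On the printed forms, 200 of 200 basic households are asked about blood and 0 of 200 enhanced households are. The share without a comparable value is 200 / 400 = 50% per round. Two possible substitutes do not fill the gap:

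- *Colour codes.* Codes 1 to 6 are not defined in the text, so nothing printed shows that any of them records blood.
- *Faecal occult blood test (Stool sampling).* It is done on 20 + 20 = 40 households per arm per round, or 40 / 200 = 20% of the arm. The other 200 − 40 = 160 enhanced households have neither a test nor a report. The test also reads one stool, collected the day after the interview, whereas the basic item is a carer's two-week report.

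**4. Diarrhoea status in the enhanced arm.** Recall period, consistency and worst-day count are all collected, so a three-stool threshold can in principle be applied. Two details are missing. No chart letter is named as loose. The single count refers to any of the stools shown, so if more than one letter applies, the count is tied to none of them.

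**5. When the status is needed.** Quotas are filled during fieldwork. The enhanced arm supplies 40 of the 80 stool donors per round, and 80 of 160 over two rounds. On the plan's assumed 10%, the expected number reporting per arm is 0.10 × 200 = 20, which equals the quota. There is then no reserve to draw on if some selected households are later found not to meet the three-stool definition. Recoding afterwards can change a donor's label, but it cannot change who was asked for stool.

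**The case against.** The strongest case on the other side has four parts.

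**The appendix is only a sample.** It is titled as a sample survey, and it also lacks the oral-intake and water-washed items that the body text promises, so the fielded form may differ. This is fair as a caution. However, the body text is consistent with the form: it too names dysentery for the basic survey alone. A reader who follows the protocol as written would not ask about blood in the enhanced arm.

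**Derived variables belong in a statistical analysis plan.** For an analysis variable this would be a full answer. It does not cover a question missing from a form, nor a status that staff must assign at the doorstep before any analysis.

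**The arms are meant to differ.** A reader might infer that the two arms use different diarrhoea definitions, so that the aim of comparing the questionnaires goes unanswered. The documents do not support that. The same recall period and a stool count are collected, so a different definition is not shown. Comparing two ways of asking is the purpose of the randomisation, and each method's predictive value may properly refer to its own positives. What stands is that the enhanced-arm definition is unstated. For the same reason no size can be put on a spurious diarrhoea ratio: the protocol gives no prevalence for looser definitions.

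**Other tempting extensions fail.** A reader might infer that dysentery can never be reported in the enhanced arm, but a carer may volunteer it. A reader might also call the absence of MUAC from the basic form an error, but the planned association with diarrhoea can be estimated within the enhanced arm, and no between-arm MUAC comparison is planned.

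**Conclusion.** The point holds in two parts.

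1. As written, the between-arm dysentery ratio lacks comparable data in about 200 of 400 households per round. The Diarrhoea survey section, the Data analysis section and Appendix 3 must be reconciled, including the sentence on clinic information. This rests on the printed enhanced form being the one used, and on no colour code standing for a report of blood. The ratio is not a primary outcome.
2. The enhanced arm has no stated rule for reporting diarrhoea, although 40 stool donors per round are selected on it in the field. This touches the primary outcomes, because the enhanced-arm positive and negative predictive values depend on that selection. How far they would be affected cannot be computed from the protocol.

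Both should be settled before fieldwork, since neither an unasked question nor the choice of stool donors can be recovered afterwards.

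**What to change.** - **Blood item.** Put the basic form's two-week blood-in-stool question, word for word, in the enhanced form after the chart questions, so that it does not colour the chart answers. Otherwise limit the between-arm comparison to diarrhoea and say so in Data analysis. In either case, reconcile the clinic-information sentence with what each form asks.
- **Case rule.** Name the chart categories that count as loose or watery and tie the worst-day count to them. Have ODK calculate enhanced-arm status as three or more such stools on the worst day in the past two weeks, and show the result to the research assistant for stool selection. Keep broader chart definitions as secondary, so that what the enhanced tool adds can still be seen.
- **Consistency of the documents.** Bring Appendix 3 into line with the oral-intake and water-washed items that the Diarrhoea survey section promises for the enhanced survey.

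The cost is a few survey items and one calculated field before fieldwork, and about a minute more per enhanced interview.
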